### **15.4 Sample Size**

A sample size of 48 (24 trans women and 24 trans men) allows detection of a difference of 0.52 log difference (1.68 fold difference) in TFV-DP from dried blood spots with 81% power on a two-sided 0.05 level test at any time point between our trans participants and MSM historical controls. A difference of 0.70 log (2.0 fold difference) can be detected between either group (trans men or women) and MSM historical controls with 80% power on a two-sided 0.05 level test. This is sufficient to determine if the differences in drug

concentrations observed in iPrEx OLE between MSM and trans women were due to interactions with feminizing hormone drug-drug interactions.

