## **4 STUDY OBJECTIVES**

### **4.1 Primary Objective**

To assess pharmacokinetics for daily oral FTC/TDF in transgender women and transgender men, and to determine if FTC/TDF drug concentrations are lower among transgender women who are using hormone therapy and in transgender men who use testosterone compared to historical controls in non-transgender MSM.

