### **15.3 Analysis of Primary Endpoint**

We will compare levels of TFV-DP in dried blood spots and rates of adverse events between trans men and trans women and a group of MSM historical controls from the iPrEx OLE study. We will compare log transformed TFV-DP levels using a linear mixed effects model with factors for group (trans men v. trans women v. MSM) and times (1, 2, 3 and 4 weeks after initiation) and their interaction with an unstructured covariance across visits and test for differences at between groups at each time point. If values appear to violate the normal distribution, we will obtain p-values and confidence intervals using the bootstrap. All p-values will be two-sided with p-value < 0.05 considered statistically significant. Adverse events will be compared using the Fisher exact test.

Adverse event rates will be coded by body system and MedDra classification term. Adverse events will be tabulated and will include the number of patients for whom the event occurred, the rate of occurrence, and the severity and relationship to study drug.

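### The leading power figure (81% at 0.52 log) belongs to a pooled trans v MSM contrast that section 15.3 does not name; each trans-group v MSM test has about 55% power there

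*Combined protocol and SAP*

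**What the plan says.** Section 15.4 makes two power statements, and the synopsis (Rationale for Number of Participants) repeats both.

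- First: "A sample size of 48 (24 trans women and 24 trans men) allows detection of a difference of 0.52 log difference (1.68 fold difference"). The sentence then states its power and its comparison: "with 81% power on a two-sided 0.05 level test at any time point between our trans participants and MSM historical controls".
- Second: "A difference of 0.70 log (2.0 fold difference) can be detected between either group (trans men or women) and MSM historical controls"; the stated power is 80%, again two-sided at 0.05.

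The analysis in 15.3 is described as follows: "linear mixed effects model with factors for group (trans men v. trans women v. MSM) and times (1, 2, 3 and 4 weeks after initiation"), plus the group-by-time interaction. The plan is to "test for differences at between groups at each time point". The primary objective in 4.1 names both comparisons: "lower among transgender women who are using hormone therapy and in transgender men who use testosterone compared to historical controls in non-transgender MSM".

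Neither the standard deviation of log TFV-DP nor the number of MSM controls is stated.

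**The concern.** The first figure a reader meets is the power of a comparison that the analysis section does not list. It combines the two trans groups, whereas 15.3 separates them and 4.1 asks about each. The synopsis rationale also treats feminizing hormones in trans women and masculinizing hormones in trans men as two questions. Section 15.4 closes by calling the sample sufficient to settle the trans women v MSM question, which is a question about one group.

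What is at stake is how a null result is read. Someone who takes 81% at 1.68-fold as the sensitivity of the trial would think that a true effect of that size in trans women, or in trans men, is missed 19% of the time (100% − 81%). For the tests that are planned, the miss rate is about 45%.

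**Working it through.** **Inputs, all from 15.4.** 48 participants, 24 per trans group; 0.52 log at 81% power for all trans participants v MSM; 0.70 log at 80% power for either group v MSM; two-sided 0.05 at a single time point. The logs are natural: exp(0.52) = 1.68 and exp(0.70) = 2.01, which match the stated fold differences.

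**Can the 81% be reproduced?** Not directly, because the SD and the number of controls are missing. The standard error (SE) behind each statement can be back-solved by the normal approximation, SE = difference / (z for 0.975 + z for power):

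- First statement: 0.52 / (1.960 + 0.878) = 0.183.
- Second statement: 0.70 / (1.960 + 0.842) = 0.250.

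**Do the two statements fit together?** The variance ratio is (0.250 / 0.183)², or 1.86 before rounding the SEs. Halving the trans arm from 48 to 24 against a fixed control group must give a ratio below 2, so they do. One pair of values that satisfies both is about 293 controls and an SD of about 1.18. The control number is very sensitive to rounding of the stated figures (about 113 to over 1,700).

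**Is the 81% the pooled figure?** If 0.52 log at 81% referred to one group of 24, power at 0.70 log would be Φ(0.70/0.183 − 1.960), about 97%, not the stated 80%. The wording and the arithmetic both make it the pooled comparison.

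**Power of each trans group v MSM at 0.52 log.** From the second statement alone, with no assumed SD or control number: Φ(0.52/0.250 − 1.960) = Φ(0.121) = 54.8%. Rounding of the stated figures moves this between 54% and 57%.

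**Sensitivity, calibrating on the 81% sentence instead.** The control number is now an assumption. The SD is solved so that 48 v controls has 81% power at 0.52 log.

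| Assumed MSM controls | Implied SD | 24 v MSM, 0.52 log | 24 v MSM, 0.70 log |
|---|---|---|---|
| 100 | 1.04 | 59% | 84% |
| 200 | 1.14 | 56% | 81% |
| 300 | 1.18 | 55% | 80% |
| unlimited | 1.27 | 52% | 77% |

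The rows with 200 to 300 controls come closest to the protocol's own 80% at 0.70 log, and there power at 0.52 log is 55% to 56%.

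**Trans men v trans women.** The three-level factor in 15.3 also implies this comparison of 24 with 24. At 0.52 log its power is about 33% at an SD of 1.18, and 29% to 41% over unlimited down to 100 assumed controls.

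**The case against.** The strongest reply is that the right figure is already printed. The sentence directly after the 81% gives 0.70 log at 80% for either group, in 15.4 and in the synopsis, and the two comparisons are labelled differently. The closing claim of sufficiency in 15.4, about trans women, follows that per-group sentence. This stands: nothing is concealed, and 55% at 0.52 log is the stated 80% at 0.70 log moved along the same power curve. Nor do the documents designate 0.52 log as a difference that must be detected in each group.

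A second reply is that the synopsis states its primary objective as interactions with cross-sex hormone therapy, without splitting the groups. A pooled contrast is consistent with that wording and could be estimated from the three-group model. Section 15 also promises a detailed SAP before the final analysis. This narrows the point without removing it. The contrast could be added, but 15.3 does not name it, and 4.1 words the objective by group.

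A reader might also infer that the plan will dilute or cancel the effect of one hormone class by averaging it with the other. The documents do not support that, because the pooled test is not among the planned analyses. It is only a reason to keep such a test supportive if it is added.

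**Conclusion.** The point holds as a mismatch between the power statement and the planned analysis. The leading 81% at 1.68-fold describes a pooled contrast that 15.3 does not name and 4.1 does not ask for. Each trans-group v MSM test has about 55% power at that difference (52% to 59% over the assumed control numbers). The 55% rests on the protocol's own 0.70 log at 80%, the normal approximation, an unadjusted two-sided 0.05 at one time point, and all 24 per group being analysed. Section 15.1 restricts the pharmacokinetic set to participants who receive every dose, so exclusions that are not replaced would lower it.

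Two stronger readings should be resisted. One is that 15.4 contains an arithmetic error: the two statements are compatible with one SD and one control number, and neither is shown to be wrong. The other is that every planned test has 55% power: that applies to the two group v MSM tests only, and trans men v trans women is lower. The severity is should-fix, since sample size, model and planned tests are unaffected.

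**What to change.** In 15.4 and in the synopsis, make the 24-per-group figure the design statement (0.70 log, 2.0-fold, 80% power for each trans group v MSM). Add that power at 0.52 log (1.68-fold) is about 55% for each of these tests. Then either delete the pooled sentence, or keep it only if 15.3 names the pooled trans v MSM contrast as a supportive analysis. Giving the SD and the number of MSM controls alongside would let a reader check the figures.

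The cost is one or two sentences in each place and a less favourable headline detectable difference. Enrolment and conduct do not change.

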## 2.2 Overview of Clinical Studies

There have been a large number of trials conducted with Truvada PrEP, including several demonstration projects. While there is no evidence to suggest that TDF/FTC interacts with commonly used feminizing or masculinizing hormone regimens, and evidence from studies of ARV interactions with hormonal contraceptives have been reassuring, no direct study of these interactions has been conducted to date.

Our team led the only trans-specific sub analysis to date of the iPrEx randomized controlled trial (RCT) data as well as the open label extension (OLE) study, which included periodic dried blood spot (DBS) drug level monitoring [2]. In iPrEx, gender identity data was not collected using current best practices (“two-step” method [5]), making the identification of transgender participants in this multinational, multicultural and multilingual trial difficult. As all iPrEx participants had been assigned male sex at birth, a transgender subgroup of 339/2499 participants (14% of overall sample) was constructed comprised of the 29 (1%) who identified as women, 296 (12%) who identified as “trans”, and 14 (1%) who reported use of feminizing hormones. None had undergone gender affirming genital surgery. Compared with MSM, transgender women more frequently reported transactional sex, receptive anal intercourse without a condom, or more than 5 partners in the past 3 months. Excluding those with a male identity who also used feminizing hormones, trans- and woman-identified participants were less likely to have TDF levels detected on random testing in the RCT (OR=0.39, 95% CI = 0.16 to 0.96, p=0.04). While there was no effectiveness of PrEP for transgender women on an intention-to-treat basis, none of the transgender participants who seroconverted had detectible drug levels at the time of HIV diagnosis. In comparison to MSM in the OLE, transgender participants had less time with protective drug concentrations (17% vs 35%, p<0.001) and were less likely to have concentrations indicating > 3 tablets/week (OR 0.71, 95% CI 0.49 to 1.03, p=0.07). Of the two transgender women who seroconverted during the OLE, both had drug levels below 350 fmol/punch in DBS, the level associated use of 2 tablets per week at the time of seroconversion. The lower concentrations were more likely if the transgender women used feminizing hormones.

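### Section 15.4 calls the sample size sufficient to settle whether feminizing hormones caused the iPrEx OLE differences, but the stated power supports only detecting about a 2-fold or larger difference, and a non-significant test alone cannot supply the negative answer

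*Combined protocol and SAP*

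**What the plan says.** Section 15.4 makes two power statements, both for two-sided 0.05 tests. The first gives 81% power for 0.52 log (1.68-fold) with all 48 participants, that is, "between our trans participants and MSM historical controls". The second concerns one group of 24: "A difference of 0.70 log (2.0 fold difference) can be detected between either group (trans men or women) and MSM historical controls", with 80% power. The section then concludes: "This is sufficient to determine if the differences in drug" concentrations seen in OLE between MSM and trans women were caused by feminizing-hormone interaction.

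Section 15.3 fits a group-by-time mixed model to log TFV-DP at weeks 1 to 4 and will "test for differences at between groups at each time point". Its decision rule is: "All p-values will be two-sided with p-value < 0.05 considered statistically significant". Confidence intervals are mentioned once, for use if normality fails: "we will obtain p-values and confidence intervals using the bootstrap". Nothing is said on how an interval or a non-significant result will be read.

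The primary objective in Section 4.1 is in part "to determine if FTC/TDF drug concentrations are lower among transgender women who are using hormone therapy" than in MSM historical controls. Section 15 promises a detailed SAP before the final analysis.

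**The concern.** Settling whether the OLE differences were due to hormones requires the study to be able to answer both yes and no. Power at 2-fold describes the chance of a significant result if the true difference is that large. It does not say what a non-significant result rules out.

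The larger and better-powered comparison does not help. It averages trans women on feminizing hormones with trans men on testosterone, so it is not specific to feminizing hormones.

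If the trans women v MSM tests are not significant, the 15.4 sentence invites the conclusion that hormones were not the cause. That would be the study's main answer to its primary question. Section 3 describes concern about PrEP and hormone therapy as the main barrier to PrEP uptake among trans women, so a null result will be read closely.

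**Working it through.** **Inputs from Section 15.4.** n = 24 trans women; 0.70 log at 80% power; 0.52 log at 81% power for 48; two-sided alpha 0.05. The SD and the number of MSM controls are not given. The single-time-point wording stands only in the sentence on 48. Applying it to the groups of 24 is an inference from the tests at each time point in 15.3.

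**The plan's own figures.** exp(0.52) = 1.68 and exp(0.70) = 2.01, so the logs are natural (base 10 would give 3.31 and 5.01). The stated power cannot be reproduced independently without the SD and control number, but the two statements can be checked against each other:
- SE for 48: 0.52/(1.960 + 0.878) = 0.183
- SE for 24: 0.70/(1.960 + 0.842) = 0.250
- SD² = 48 × (0.250² − 0.183²), computed unrounded, giving an SD of about 1.18 and about 293 controls. Rounding of the stated figures allows an SD of 1.12 to 1.23 and 146 to 1,727 controls.

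The statements are therefore mutually consistent, and the planning SE for trans women v MSM is about 0.25.

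**Power at one time point**, Φ(ln(fold)/0.250 − 1.96):

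| True fold difference | ln | Power |
|---|---|---|
| 2.01 | 0.700 | 80% |
| 1.68 | 0.519 | 55% |
| 1.5 | 0.405 | 37% |
| 1.25 | 0.223 | 14% |

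**What a non-significant result would exclude.** The 95% CI factor is exp(1.96 × 0.250) = 1.63.
- Observed ratio 1.00: CI 0.61 to 1.63. A halving is excluded; reductions of up to 39% are not.
- Observed ratio 0.70: z = −0.357/0.250 = −1.43, p = 0.15, CI 0.70/1.63 = 0.43 to 0.70 × 1.63 = 1.14. A halving is not excluded.

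**Is there an OLE benchmark?** Section 2.2 gives 17% v 35% of time with protective concentrations, and an odds ratio of 0.71 for levels indicating more than 3 tablets a week. Section 2 gives an odds ratio of 0.14 for protective levels, hormone users v non-users, within trans women in iPrEx. None is a concentration ratio. Turning them into one needs assumptions (log-normal levels, equal SDs, an assumed SD; for 0.14 also 20% to 50% of non-users protected):

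| Summary | Assumed SD | Implied fold | Power at SE 0.25 |
|---|---|---|---|
| 17% v 35% | 1.04 to 1.24 | 1.8 to 2.0 | 66% to 81% |
| OR 0.71 | 1.04 to 1.24 | 1.2 to 1.3 | 12% to 15% |
| OR 0.14 | 1.12 to 1.23 | 3.0 to 4.2 | above 99% |

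The range runs from poorly powered to almost certain, and the gaps may be partly behavioural, as Section 2 says.

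**Sensitivity to the SE.** With an assumed SD of 0.5 and 100 to 293 controls (also assumed), SE = 0.5 × √(1/24 + 1/m) = 0.114 to 0.106. Power is then 95% to 97% at 1.5-fold and 50% to 56% at 1.25-fold, and the CI factor is 1.25 to 1.23.

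**The case against.** A reader might infer that the trial is too small. The documents do not support that. Section 15.4 speaks of the differences seen in OLE, not of every possible interaction, and for a true difference of 2-fold or more the power is about 80% or higher. Low power at 1.5-fold counts against the sentence only if the OLE gap was that small, and its size on the concentration scale is not stated. The within-trans-women odds ratio of 0.14 points to a large gap. This stands: insufficiency is not shown. Nor is sufficiency, and that is what the sentence asserts.

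A reader might also infer that the study can never answer no. That goes too far: at the planning SE an observed ratio of 1.00 excludes a halving.

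The SE of 0.25 is a planning value. Trans participants are dosed under observation, and Section 15.1 limits the PK analysis to those who receive all doses, so the realised SE may be smaller. That would improve precision, but p ≥ 0.05 would still not show absence of interaction.

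Four weekly tests raise the chance of some significant result. For a true 1.5-fold difference, simulation at an assumed between-visit correlation of 0.5 to 0.9, without adjustment, gives about 67% to 50%; with no difference it gives about 16% to 9%. This helps detection at the price of more false positives and does nothing for a negative conclusion.

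Finally, 15.3 nowhere says that non-significance will be read as no interaction. The bootstrap sentence may well describe a substitute method for intervals that the model would also give, and the SAP can carry the detail. All this is fair, but no rule for reading a null result is yet written, and the 15.4 sentence encourages the wrong one.

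**Conclusion.** The concern holds in a limited form. The stated power supports detecting about a 2-fold or larger difference for trans women v MSM. It does not support the claim that the size can determine whether the OLE differences were due to feminizing hormones, and a non-significant test alone cannot support the answer that they were not. At the planning SE, the non-significant ratio of 0.70 shown above would leave a halving open, and even a ratio of exactly 1 would leave reductions of up to 39% open.

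This rests on the normal approximation, on reading the 24 v MSM figure as per time point, and on an SE near 0.25. The SE is the least certain of these. The point concerns precision only. Whether a difference from historical controls can be attributed to hormones is a separate question that power does not settle. The change is worth making because it governs what a null primary result may be said to show.

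**What to change.** **Section 15.4 (and the matching synopsis row).** Replace the sufficiency sentence with a statement that each trans group v MSM comparison has 80% power for about a 2-fold or larger difference, and that at the planning SE smaller interactions may be neither detected nor excluded. Add that the 0.52 log figure pools trans men and trans women and is not specific to feminizing hormones.

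**Section 15.3 and the SAP.** Report each trans group's geometric mean ratio v MSM with its 95% CI at each week. State that p ≥ 0.05 will not be read as no interaction. Conclude that there is no relevant reduction only if the lower CI limit lies above a bound chosen by the sponsor at one named time point, with both bound and time point fixed before assay results are available. Otherwise, unless a reduction is shown, report the result as inconclusive with its interval.

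**Cost.** Wording and one interpretation rule; no added participants, visits, samples or assays. The stated claim becomes less favourable, and inconclusive results may be common if the SE is near 0.25. At a true ratio of 1, the chance of meeting the rule at one time point is Φ(−ln(bound)/0.250 − 1.96): about 14% for a bound of 0.80, 37% for 0.67 (two-thirds) and 79% for 0.50. With the assumed SD of 0.5 it would be 50% to 56% for 0.80 and 95% to 97% for 0.67. These bounds are illustrations, not recommendations.

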## **16 DATA COLLECTION, RETENTION AND MONITORING**

### **16.1 Data Collection Instruments**

The Investigator will prepare and maintain adequate and accurate source documents designed to record all observations and other pertinent data for each participant treated with the study drug.

Study personnel at study site will enter data from source documents corresponding to a participant's visit into the protocol-specific database when the information corresponding to that visit is available. Participants will not be identified by name in the study database or on any study documents to be collected by the investigators, but will be identified by a site number, participant identification number (PID).

*For paper source documents:* If a correction is made on a CRF, the study staff member will line through the incorrect data, write in the correct data and initial and date the change.

The Investigator is responsible for all information collected on participants enrolled in this study. All data collected during the course of this study must be reviewed and verified for completeness and accuracy by the Investigator or his representative. A copy of the CRF and/or source documents will remain at the Investigator's site at the completion of the study for a period of 2 years after final data analysis.

### **16.2 Data Management Procedures**

The data will be entered into a validated database. The Data Management group will be responsible for data processing, in accordance with procedural documentation. Database lock will occur once quality assurance procedures have been completed.

All procedures for the handling and analysis of data will be conducted using good computing practices.

### **16.3 Data Quality Control and Reporting**

After data have been entered into the study database, a system of data validation checks will be implemented and applied to the database on a regular basis. For example, query reports pertaining to data omissions and discrepancies may be forwarded to the study site for resolution, as applicable. The study database will be updated in accordance with the resolved queries. All changes to the study database will be documented.

### **16.4 Archival of Data**

The database is safeguarded against unauthorized access by established security procedures; appropriate backup copies of the database and related software files will be maintained. Databases are backed up by the database administrator in conjunction with any updates or changes to the database.

At critical junctures of the protocol (e.g., production of interim reports and final reports), data for analysis is locked and cleaned per established procedures.

### **16.5 Availability and Retention of Investigational Records**

The Investigator must make study data accessible to the monitor, other authorized representatives of funding agencies, IRB/IEC, and Regulatory Agency (e.g., FDA) inspectors upon request. For each participant, the signed Informed Consent, HIPAA Authorization and copies of all source documentation related to that participant will be maintained. Data will be kept separate from documents containing personal identifiers. The Investigator must ensure the reliability and availability of source documents from which the information in the database was derived.

All study documents (patient files, signed informed consent forms, copies of CRFs, Study File Notebook, source logs and check lists, etc.) must be kept secured for a period of 2 years following study results analysis is done.

